1.3. Sample Size and Power

With a sample size of 320 subjects in each active treatment arm and 160 subjects in the placebo arm, the study has 94% power to detect a difference in the proportion of subjects with a ≥ 1 -stage improvement in fibrosis without worsening of NASH of 15% or more at Week 48 at a significance level of 0.025 (2-sided), assuming the proportion of subjects that meet the endpoint in the placebo arm is 12%.

With regard to the clinical efficacy endpoint, subjects will be followed for a period of up to 240 weeks. The estimate of the expected event rate is 30% in untreated patients, producing an expected EFS rate of 70% at 240 weeks in the placebo arm. SEL is expected to improve the EFS rate to 83.7% (expected event rate of 16.3%) compared with placebo (hazard ratio (HR), 0.50). We also expect a 20% overall dropout rate. Given the above assumptions, for comparison of the SEL arms versus the placebo arm, together with a total sample size of 800 subjects (2:2:1 ratio), and assuming the log-rank test statistic is evaluated using a 2-sided 0.025 significance level, the study will have 85% power to evaluate the superiority of each SEL arm versus placebo with respect to EFS.

Therefore, the overall power for the trial, assuming independence between the primary efficacy endpoint and clinical efficacy endpoint, is 80% ($94\% \times 85\%$). It should be noted that this is a lower bound estimate as these 2 endpoints are expected to be positively correlated.

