3.6. Missing Data and Outliers

3.6.1. Missing Data

For missing last dosing date of study drug, imputation rules are described in Section 4.2.1. The handling of missing or incomplete dates for AE onset is described in Section 7.1.5.3, and for prior and concomitant medications in Section 7.4.

The following imputation approaches will be applied to efficacy endpoints as specified:

1) Non-Responder Imputation (NRI)

For purpose of analysis at a defined time point, when NRI is used, all subjects with missing values will be analyzed as not meeting the corresponding endpoint. The NRI method will be applied to subjects with or without baseline value.

2) Multiple Imputation (MI):

The MI procedure replaces each missing data point of the binary primary histology efficacy endpoint (defined in Section 6.1.1) with a set of plausible values that represent the uncertainty about the right value to impute under the missing at random (MAR) assumption. The imputation model used to impute missing data points will be based on the logistic regression with the treatment arms and the 2 stratification factors as covariates. A total of 50 imputed datasets will be generated by the imputation model. That is, each missing data point will be imputed 50 times. Each imputed data set will be analyzed by the method for the primary analysis as specified in Section 6.1.3. The results from these 50 imputed data sets will be combined using Rubin's rule {[Rubin 1987](#)}.

3) Tipping Point Analysis (TPA):

If any significant result in favor of SEL 18 mg or SEL 6 mg is detected in the primary analysis of the binary primary histology efficacy endpoint (described in Section 6.1.3), a delta-adjusting pattern-mixture approach for TPA {[Ratitch 2013](#)} will be conducted to assess the robustness of the primary analysis results under a missing not at random assumption for SEL arms. Specifically, it is assumed that a systematic difference exists between the conditional distributions of the missing and observed data in the SEL arms. To reflect such a systematic difference, a shift parameter δ will be applied to the imputation model (ie, the logistic regression with the treatment arms and the 2 stratifications factors as covariates) when the missing data points in the SEL arms are imputed. For each value of δ , multiply imputed data sets will be generated, each data set will be analyzed by the same method for the primary analysis, and analysis results will then be combined by Rubin's rule. Thus, by

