
varying the values of δ , the impact from missing data on the analysis results will be examined to identify tipping points (ie, the values at which conclusions from statistical inference change from being significant to being insignificant for SEL arm(s)).

4) Last Observation Carried Forward (LOCF)

For purpose of analysis at a defined time point, if the value is missing, the last observed value prior to the time point will be used to impute the missing value. Refer to Section 3.8.2 for the handling of the data to be included in efficacy analysis. The LOCF approach will be applied to those subjects who have a baseline value. No imputation will be performed if the value at baseline is missing.

5) Observed Case (OC)

Only subjects with observed Baseline and Week 48/240 values will be included at the corresponding Week 48/240 analysis.

6) Kaplan-Meier Multiple Imputation (KMMI)

Sensitivity analysis will be performed under the KMMI strategy {Zhao 2014} if there are significant differences in the Kaplan-Meier (KM) estimates of survival rates between SEL 18 mg or SEL 6 mg and placebo. This method introduces a sensitivity parameter, θ , defined as the fixed hazard ratio of a subject who dropped out having the event after being censored at a certain centering time relative to subjects who remain on treatment having the event after that censoring time. The MAR-like assumption (ie, noninformative independent censoring) corresponds to $\theta = 1$. $\theta > 1$ implies a higher hazard after censoring for subjects who drop out compared with their counterparts who remain on treatment. By varying the values of θ , the KMMI strategy addresses departures from the MAR-like assumption when unobserved time-to-event data are multiply imputed. The KMMI approach can be summarized as follows:

- i). Calculate KM estimates of survival rates for each treatment group within each stratum separately.
- ii). Obtain the survival estimate at each censoring time by linear interpolation of the KM survival rates corresponding to the 2 event times immediately before and after. The KM survival function may be extrapolated to calculate the survival estimates at censoring time which is after the event time of the last observed event up to the maximum follow-up time (ie, 252 weeks [or 58 months]).
- iii). Apply each value of θ to impute the unobserved event time for a dropout subject who will experience the event after the time being censored for a total of 50 times.

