After the multiple imputation, the pairwise logrank test will be performed to compare the survival rates between SEL 18 mg or SEL 6 mg and placebo on each complete data set (described in Section 6.2.3). Then, by combining the normalized chi-square statistics using Rubin's rule, the impact of departures from noninformative censoring can be investigated by

the combined treatment effect inference, which is a function of θ . Thus, the robustness of the significant results can be assessed.

The NRI approach will be used for the primary analysis of the primary histology efficacy endpoint and secondary endpoints evaluated at Week 48. LOCF analysis and OC analysis will be carried out as sensitivity analyses for these endpoints at Week 48 using the same analysis method as defined in Section 6.1.3. “Last observation” includes both baseline and postbaseline records, and only the records eligible for efficacy analysis will be carried forward.

The MI and TPA approaches will be used for the sensitivity analyses for the primary histology efficacy endpoint. KMMI approach will be used for the sensitivity analysis for the clinical efficacy endpoint.

The NRI approach will be used for the primary analysis for the secondary endpoints evaluated at Week 240. The LOCF and OC approaches will be used for sensitivity analysis of these endpoints.

CCI

In the subgroup analysis by body weight change from baseline, missing Week 48/Week 240 (for the Week 48/240 analysis, respectively) body weight will be imputed using the LOCF approach to determine which subgroup a subject belongs to.

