Median, Q1 and Q3 of the EFS will be provided for each treatment group. The 95% CI for median EFS based on Brookmeyer-Crowley method {[Brookmeyer 1982](#)} of inverting a generalization of the sign test for censored data will also be provided for each treatment group.

Kaplan-Meier curves will be plotted for the clinical EFS by treatment arm. A by-subject listing of clinical events will be provided.

A sensitivity analysis of EFS will be performed where mortality includes only liver-related death. All deaths will be reviewed by the Hepatic Event Adjudication Committee to determine if they are liver-related.

In addition, a sensitivity analysis for the clinical efficacy endpoint will be performed by using the KMMI approach as described in Section 3.6.1 if the survival functions of SEL 18 mg (SEL 6 mg) and placebo are demonstrated to be significantly different (in favor of SEL 18 mg or SEL 6 mg).

Forest plots of treatment effect in the clinical efficacy endpoints, assessed by the hazard ratios between each SEL arm and placebo arm, will be generated for the Week 48 interim analysis and the Week 240 final analysis. Forest plots for subgroup analyses will be generated in the final analysis at Week 240.

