6.3. Secondary Efficacy Endpoints

6.3.1. Definition of Secondary Efficacy Endpoints

The secondary endpoints of this study are as follows:

- 1) Proportion of subjects who have progression to cirrhosis by Week 48
- 2) Proportion of subjects who have a ≥ 1 -stage improvement in fibrosis (according to the NASH CRN classification) without worsening of NASH at Week 240
- 3) Proportion of subjects who have a ≥ 1 -stage improvement in fibrosis (according to the NASH CRN classification) at Week 48 and Week 240
- 4) Proportion of subjects who have NASH resolution (defined as lobular inflammation of 0 or 1 from at least 1 at baseline and hepatocellular ballooning reduced to 0 from at least 1 at baseline; both criteria are necessary conditions) without worsening of fibrosis (according to the NASH CRN classification) at Week 48 and Week 240

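### Progression to cirrhosis by Week 48: the primary missing-data rule scores a missing biopsy as no cirrhosis, which is the favourable outcome

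*SAP*

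**What the plan says.** SAP Section 3.6.1 defines NRI by what happens to the endpoint, not by whether the outcome is good or bad: "all subjects with missing values will be analyzed as not meeting the corresponding endpoint". The same section sets its scope: "The NRI approach will be used for the primary analysis of the primary histology efficacy endpoint and secondary endpoints evaluated at Week 48". The first secondary endpoint in Section 6.3.1 is "Proportion of subjects who have progression to cirrhosis by Week 48", and no exception is made for it. Section 3.8.3 names progression to cirrhosis among the histology endpoints that go to Section 3.6.1 when they cannot be derived from any biopsy in the window. Section 6.1.3 treats missing data as treatment failure, but only for the primary histology endpoint.

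Two sensitivity analyses are planned for the Week 48 secondary endpoints. Under LOCF, "the last observed value prior to the time point will be used to impute the missing value", and baseline counts as an observation. The observed-case (OC) analysis drops subjects with missing values. The stronger methods are reserved: "The MI and TPA approaches will be used for the sensitivity analyses for the primary histology efficacy endpoint".

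Table 3-6 sets the Week 48 biopsy window at Days 169 to 504. A post-baseline biopsy on Days 2 to 168 has no window, although Section 3.8.2 says all biopsy data are mapped.

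**The concern.** For fibrosis improvement and NASH resolution, NRI is conservative for each subject, because a missing biopsy is scored as failure. Progression to cirrhosis is an adverse event, so the same sentence works the other way and every missing biopsy is credited as no progression. LOCF does not correct this: eligibility requires F3, so a subject with no post-baseline biopsy carries F3 forward and is again scored as free of cirrhosis.

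The endpoint addresses the part of the primary objective that concerns reducing progression to cirrhosis. Section 6.3.2 reports its estimate, confidence interval and p-value. That estimate moves with the missing fraction in each arm, and missing biopsies are plausible because the early-termination biopsy is at the investigator's discretion (Protocol Section 6.4.6).

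A narrower gap adds to this. Read literally, a central-read F4 on Days 2 to 168 with no later in-window biopsy is missing, and so scored as no progression, although event-free survival (EFS) counts it (SAP Section 6.2.1). A subject who stays in the Randomized Phase is still due a Week 48 biopsy. One who rolls over to open label is not (Protocol Appendix 2, footnote d), and SAP Section 6 excludes open-label data from efficacy.

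**Working it through.** **Plan's own figure.** The documents state no figure for this endpoint. The nearest is 94% power for the primary histology endpoint (27% vs 12%, 320 vs 160, two-sided 0.025). It reproduces as 94.0% with a continuity correction and 95.4% without, which confirms the arm sizes used below.

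**Bias formula.** Let p be the progression risk (taken as the same in missing and observed subjects) and m the missing fraction, with S for SEL and P for placebo. NRI scores the rate p(1 - m). Therefore

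bias = NRI difference - true difference = pP·mP - pS·mS.

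**Assumed risks.**
- 6.9%: SAP Section 1.3 says "The estimate of the expected event rate is 30% in untreated patients" over 240 weeks for the whole composite. At constant hazard, 1 - 0.70^(48/240) = 0.0689. Scheduled biopsies could concentrate detection at Week 48.
- 20%: 2 of 10 on simtuzumab alone in Phase 2 at Week 24 (Protocol Table 1-1).
- 15%: intermediate.

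**No true effect.** Rejection is the exact sum over the joint binomial (320, 160) of outcomes with z < -1.96, using the Section 6.1.3 standard error and one stratum. Cells show the difference in points and the chance of nominal significance favouring SEL.

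| Missing SEL / placebo | Risk 6.9% | Risk 15% | Risk 20% |
|---|---|---|---|
| none | 0; 1.65% | 0; 2.00% | 0; 2.10% |
| 4.9% / 2.45% | -0.17; 1.95% | -0.37; 2.58% | -0.49; 2.83% |
| 10% / 5% | -0.34; 2.31% | -0.75; 3.35% | -1.0; 3.83% |
| 20% / 10% | -0.69; 3.24% | -1.5; 5.51% | -2.0; 6.81% |
| 20% / 5% | -1.03; 4.52% | -2.25; 8.57% | -3.0; 11.12% |
| 10% / 20% | +0.69; 0.68% | +1.5; 0.55% | +2.0; 0.46% |

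Example: at 15% risk and 20%/10% missing, the scored rates are 0.15 × 0.80 = 12.0% and 0.15 × 0.90 = 13.5%. A separate simulation of the stratified test (four strata, assumed shares 35/35/15/15%) gave 5.2% at 15% risk and 6.4% at 20% risk for 20%/10% missing. Observed-case scoring in the same runs gave a mean difference near zero and 1.9% to 2.1%, with missingness unrelated to progression.

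**True effect.**
- Hazard ratio 0.50 on 6.9% (SEL 1 - 0.9311^0.5 = 3.50%): the true -3.4 points becomes -3.0 with 10% missing in both arms, -2.7 with 20% in both, -3.4 at 20%/10% and -3.7 at 20%/5%.
- 7.5% vs 15%: the true -7.5 becomes -6.75, -6.0, -7.5 and -8.25 in the same four cases. Break-even at 20%/10%: 0.15 × 0.10 - 0.075 × 0.20 = 0.
- 7.4% vs 20% (Phase 2 rates): at 20%/10% the bias is 0.20 × 0.10 - 0.074 × 0.20 = +0.52 points, so -12.6 becomes -12.1. SEL is penalised despite having more missing data.

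**Opposite bound.** Scoring missing as progressed, with no true effect and 20%/10% missing, gives +9.3, +8.5 and +8.0 points at the three risks.

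**Early F4.** Each lost Day 2 to 168 F4 moves a SEL arm by 1/320 = 0.31 points and placebo by 1/160 = 0.63 points.

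**The case against.** The strongest objection is to size. The only dropout figure, 20%, belongs to the 240-week EFS calculation. Converted at constant hazard, as the event rate was, it is 1 - 0.8^(48/240) = 4.4% by Week 48. A twofold imbalance around that (4.9% vs 2.45%) gives the second row of the table, close to the nominal 2.5% per side. Early discontinuation was rare: 3 of 425 treated subjects had stopped drug at a median of 11.9 weeks (Protocol Section 1.2.10.1). Nothing in the documents supports 20% vs 5%, and the 20% risk rests on 10 subjects in an open-label study. This stands as a limit on magnitude, although refused or unevaluable biopsies would add to dropout.

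Second, the direction is not fixed. This also stands, and the true-effect results show it.

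Third, much is already covered. OC is planned, the endpoint is outside the alpha scheme of SAP Section 3.5, and Section 6.2.3 provides "Forest plots of treatment effect in the clinical efficacy endpoints, assessed by the hazard ratios between each SEL arm and placebo arm" at Week 48; it also says "A by-subject listing of clinical events will be provided". These outputs show early F4s and deaths, but within a composite that censors subjects without an event. The Kaplan-Meier multiple imputation varies the hazard after dropout, but only for EFS and only after a significant result.

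Fourth, parts of Sections 3.6.1 and 6.4 are redacted, so the absence of a stress test for this endpoint can be asserted only for the visible text. Fifth, the early-F4 case is remote: no biopsy is scheduled then, and LOCF may recover the record if it is eligible.

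None of this changes what the primary rule does to a missing biopsy.

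**Conclusion.** The concern holds. As written, the primary analysis of this endpoint assigns the good outcome to every missing biopsy, and no visible planned analysis of it scores missing as progression or tests departures from missing at random. At equal risk the arm with more missing biopsies benefits; with equal missingness a true effect shrinks by the factor 1 - m; if SEL halves the risk, SEL gains only when its missing fraction is more than twice that of placebo.

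The size depends on missing rates and risks that the documents do not give, and on equal risk in missing and observed subjects. It is negligible at about 5% vs 2.5% missing and material at 20% vs 10% or beyond. The reading of the text is firm; the magnitude is conditional. Because the endpoint gates nothing and OC is planned, this belongs at the lower end of what should be fixed.

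**What to change.** Amend the SAP for this endpoint only:

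1. Count as progressed any central-read F4 on a Randomized Phase biopsy from first dose to the end of the Week 48 window, including Days 2 to 168.
2. Replace NRI as primary handling with the planned OC analysis, or with the Section 3.6.1 multiple imputation extended to this endpoint. The two will be close, because the imputation model uses only arm and strata. OC drops subjects from the Full Analysis Set; multiple imputation keeps them. Both assume missingness is uninformative given the model.
3. Add one sensitivity analysis: missing scored as progressed, or a tipping-point run using the Appendix 8 macro with positive shifts for the SEL arm, since here the event is harm.

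No separate analysis of death, transplant or decompensation is needed; EFS largely covers these.

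The cost is SAP wording and a few extra runs, with no new data. The macro hard-codes the primary endpoint variable, so that must be swapped, and as printed it has one more %end than %do. Two downsides should be stated in the SAP: this endpoint's primary handling will differ from that of the other Week 48 secondary endpoints, and item 1 overrides the closest-to-nominal-day selection rule, so an arm with more for-cause biopsies has more chances to record an F4.

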2.2. Interim (Week 48) Analysis

When all subjects have completed the Randomized Phase Week 48 visit, or have a clinical event before Randomized Phase Week 48 visit, or have prematurely discontinued from the study, superiority of each SEL arm relative to the placebo arm will be assessed with respect to the primary histology efficacy endpoint.

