- For baseline, the last available record on or prior to the date of the first dose of study drug will be selected in the corresponding phase. If there are multiple records on the same day, the value with the lowest severity will be selected (eg, normal will be selected over abnormal for safety electrocardiogram [ECG] findings).
- For postbaseline visits, if there are multiple records on the same day, the value with the worst severity within the window will be selected (eg, abnormal will be selected over normal for safety ECG findings).

Postbaseline parameters used to define histology endpoints will be selected in each visit window according to the following rules:

- Histology endpoints including a ≥ 1 -stage improvement in fibrosis without worsening of NASH, progression to cirrhosis, ≥ 1 -stage improvement in fibrosis, NASH resolution without worsening of fibrosis, NAS and elements, SAF and elements will be derived based on parameters collected from 1 biopsy sampling date if the following 4 parameters are available: NASH CRN fibrosis stage, lobular inflammation, hepatocellular ballooning, and steatosis grades.
- When the set of the 4 parameters (NASH CRN fibrosis stage, lobular inflammation, hepatocellular ballooning, and steatosis grades) is available for multiple biopsy samples obtained on different dates in 1 visit window, the set with the biopsy sample collection date closest to the nominal day will be chosen for analysis.. When 2 samples are equidistant from the nominal day, the later set will be selected.
- When the set of the 4 parameters is not complete for any biopsy sample from a single day, the histology endpoints will be derived based on the nonmissing value of each individual parameter closest to the nominal day for that visit window. When 2 records are equidistant from the nominal day, the later record will be selected.
- For Ishak fibrosis stage, the nonmissing value from the biopsy sample collection date closest to the nominal day for the visit window will be selected regardless of the missing status of other parameters. When 2 records are equidistant from the nominal day, the later record will be selected.
- When an endpoint cannot be derived based on all biopsy samples in a visit window, the histology endpoint will be considered missing, and imputation methods listed in Section 3.6.1 will apply.

Liver stiffness by transient elastography data in each analysis visit window will be chosen based on the following rules:

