Appendix 8. SAS Program for Tipping Point Analysis for Binary Endpoint

The following **%tp_binary** macro generates multiple imputed data and a set of the shift parameters that adjust the imputed values will be examined.

```

/*-----*/
/*--- Delta-Adjusting Method for Tipping Point Analysis for Binary Endpoint ---*/
/*--- Generate imputed data set for specified shift parameters ---*/
/*--- data= input data set ---*/
/*--- smin= min shift parameter for active drug ---*/
/*--- smax= max shift parameter for active drug ---*/
/*--- sinc= increment of the shift parameter for active drug ---*/
/*--- trt= treatment group indicator ---*/
/*--- out= output imputed data set ---*/
/*-----*/

%macro tp_binary( data=, smin=, smax=, sinc=, trt=, out=);
  data &out;
  set _null_;
  run;

  /*----- # of shift values -----*/
  %let ncase= %sysevalf( (&smax-&smin)/&sinc, ceil );

  /*----- Imputed data for each shift -----*/
  %do jc=0 %to &ncase;
    %let sj= %sysevalf( &smin + &jc * &sinc);

    proc mi data=&data seed=20190000 nimpute=50 out=outmi;
      var trt01pn strat1V strat2V pe48;
      class trt01pn strat1V strat2V pe48;
      monotone logistic (pe48 / link=logit);
      mnar adjust( pe48(event='1') / adjustobs=(trt01pn="&trt") shift= &sj);
    run;

    data outmi;
    set outmi;
    Shift_Trts= &sj;
    run;

    data &out;
    set &out outmi;
    run;

  %end;
%end;
%mend tp_binary;

```

SAP GS-US-384-1943

ELECTRONIC SIGNATURES

Signed by	Meaning of Signature	Server Date (dd-MMM- yyyy hh:mm:ss)
PPD	Clinical eSigned	23-Jan-2019 21:31:31
PPD	Biostatistics eSigned	25-Jan-2019 02:05:16

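### Multiple imputation and the tipping-point analysis give subjects with no Week 48 biopsy because of death, transplant, decompensation or early F4 their arm's chance of response, although the primary analysis counts them as failures

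*SAP*

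**What the plan says.** SAP 3.6.1, item 2, states that "The MI procedure replaces each missing data point of the binary primary histology efficacy endpoint" under missing at random. The model contains the treatment arms and the two stratification factors (diabetes and ELF category). Item 3, the tipping-point analysis, uses the same model with a shift on SEL, and runs only after a significant primary result in favour of SEL. The Appendix 8 macro lists "var trt01pn strat1V strat2V pe48" and applies the shift to the one selected arm. Clinical-event status appears in neither the text nor the code.

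SAP 2.2 foresees subjects who complete Week 48, "or have a clinical event before Randomized Phase Week 48 visit", or discontinue. SAP 3.8.3 says that when the endpoint cannot be derived from any biopsy in the window, "the histology endpoint will be considered missing, and imputation methods listed in Section 3.6.1 will apply". In SAP Table 3-6 the Baseline window ends on Day 1 and the Week 48 window runs from Day 169 to Day 504. SAP 3.8.2 windows every biopsy taken before open-label Study Day 1.

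No later biopsy fills the gap. A subject with a confirmed event leaves the Randomized Phase (Protocol 3.3.1), and a transplanted subject leaves the study (Protocol 6.7). No biopsy is done in the Open-Label Phase (Protocol Appendix 2, footnote d), and SAP section 6 excludes data from the first open-label dose onward.

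The primary analysis (SAP 3.6.1 and 6.1.3) counts every missing Week 48 result as a failure.

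**The concern.** For a biopsy missed for unrelated reasons, missing at random given arm and strata is a reasonable relaxation of non-responder imputation. It is not reasonable when the biopsy is absent because the subject died, was transplanted, decompensated, or had already reached F4. Arm and strata do not explain that absence, and the model treats the subject as exchangeable with those who stayed well enough to be biopsied.

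The plan then handles the same subject in five ways:

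| Analysis | Subject with no windowed biopsy because of an event |
|---|---|
| Primary (non-responder imputation) | Failure |
| Last observation carried forward | Failure, since baseline F3 or an early F4 is carried forward |
| Observed case | Left out |
| Multiple imputation | The arm's response probability |
| Tipping point | The arm's response probability, shifted on the selected SEL arm only |

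At stake is how well two robustness analyses of the primary endpoint can be read. Because the imputed probability is higher on SEL, each SEL event adds more to the SEL rate than a placebo event adds to placebo.

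**Working it through.** **1. Inputs (SAP 1.3).** "With a sample size of 320 subjects in each active treatment arm and 160 subjects in the placebo arm, the study has 94% power" for a difference in "improvement in fibrosis without worsening of NASH of 15% or more at Week 48", with placebo at 12% (so SEL at 27%) and two-sided alpha 0.025. For the clinical endpoint, "The estimate of the expected event rate is 30% in untreated patients" by Week 240, and 16.3% on SEL (hazard ratio 0.50).

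**2. The plan's power figure.** Pooled rate = (160 × 0.12 + 320 × 0.27)/480 = 0.22. Null SE = √(0.22 × 0.78 × (1/160 + 1/320)) = 0.0401. Alternative SE = √(0.12 × 0.88/160 + 0.27 × 0.73/320) = 0.0357. Power = Φ((0.15 − 2.241 × 0.0401)/0.0357) = 95.4%. With a continuity correction of 0.5 × (1/160 + 1/320) it is 94.0%, so the stated 94% is reproduced and the design rates can be used.

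**3. Who is affected.** Death, transplant, or a confirmed event with rollover is affected if there is no biopsy between Day 169 and open-label Day 1. F4 found on Days 2 to 168 falls in no window, so it is affected if no later windowed biopsy exists. F4 found from Day 169 and before open-label Day 1 is an observed non-response and is not imputed.

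**4. How many, at the plan's rates.** The documents give no Week 48 event rate, so I assume constant hazard. Placebo: 1 − 0.70^(48/240) = 6.9%, or 11.0 of 160. SEL: 1 − 0.837^(48/240) = 3.5%, or 11.2 of 320. These are upper bounds at those rates, because they include F4 first seen at the Week 48 biopsy itself.

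**5. Effect on multiple imputation.** Let r be the arm's response rate with missing counted as failure, and m the affected share. With no other missing values and ignoring strata, the observed rate is r/(1 − m). Affected subjects are imputed at that rate, so the arm's imputed rate is also r/(1 − m). In the upper-bound case:

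- SEL: 0.27/(1 − 0.0350) = 28.0%, crediting about 11.2 × 0.280 = 3.1 responders per imputed data set.
- Placebo: 0.12/(1 − 0.0689) = 12.9%, crediting about 11.0 × 0.129 = 1.4.
- Difference: 15.1 points, against 15.0 when these subjects are failures.

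**6. Effect on the tipping-point analysis.** With shift δ, the difference is r_SEL + m_SEL × q(δ) − r_PBO/(1 − m_PBO), where logit q(δ) = logit(r_SEL/(1 − m_SEL)) + δ. Placebo is never shifted.

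| Affected share, SEL / placebo | Multiple imputation (δ = 0) | δ = −1 | δ = −2 | δ very negative |
|---|---|---|---|---|
| 3.5% / 6.9% (plan rates, upper bound) | 15.1 | 14.5 | 14.3 | 14.1 |
| 2% / 2% (assumed) | 15.3 | 15.0 | 14.9 | 14.8 |
| 5% / 5% (assumed) | 15.8 | 15.0 | 14.6 | 14.4 |
| 5% / 10% (assumed) | 15.1 | 14.3 | 13.9 | 13.7 |
| 10% / 5% (assumed) | 17.4 | 15.7 | 14.9 | 14.4 |

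Entries are differences in points. With the affected subjects fixed as failures, every cell would be 15.0. With equal shares the sign changes near δ = logit(0.12) − logit(0.27) = −1.0. Milder shifts favour SEL and stronger ones go against it.

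**The case against.** Several stronger readings are tempting, and the documents do not support them.

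- *Progression to F4 in general is imputed away.* It is not. F4 needs a centrally read biopsy (SAP 6.2.1), and from Day 169 to open-label Day 1 that biopsy is the observed Week 48 result. Only F4 on Days 2 to 168 with no later windowed biopsy is affected. A decompensated subject biopsied from Day 169 and before open-label Day 1 is likewise observed.
- *The shift needed to tip the result looks larger than it is.* The direction is not uniform, and usually it is the reverse, because placebo subjects keep their unshifted chance of response. In an approximate unstratified calculation with SEL at 21%, placebo at 12%, 10% other missing values and 2% affected in each arm (assumptions), the written plan tips at a shift of about −1.2 and the corrected one at about −1.6. The written plan is more lenient mainly when SEL has clearly more events. At the design rates neither version tips.
- *All the robustness analyses share the fault.* Last observation carried forward already gives non-response. Observed case leaves these subjects out by definition, and adding unobserved failures would make it a different analysis.
- *These outcomes are failures by definition.* That is literal only for F4. The endpoint in SAP 6.1.1 is purely histologic, and death or decompensation becomes a failure only through the missing-data rule.

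The other side can also say that the effect is negligible. The cited F3 liver-event risk of 14% over a median of 12.6 years (Protocol 1.4.1) is about 1 − 0.86^(48/(12.6 × 52.18)) = 1.1% per 48 weeks at constant hazard. Blinded data on 425 treated subjects showed no deaths at a median of 11.9 weeks (Protocol 1.2.10). This stands as to size. It does not supply the missing rule, and the near-cancellation at the plan's rates depends on SEL halving events, which the trial has yet to show.

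**Conclusion.** The gap is real and minor. As written, multiple imputation and the tipping-point analysis give subjects without a windowed biopsy because of death, transplant or decompensation with rollover, or with F4 only on Days 2 to 168, their arm's chance of response. The primary analysis scores them as failures.

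The confirmatory test is untouched, and nothing here suggests that a significant result would be false. The multiple-imputation difference is inflated by about 0.1 point at the plan's event rates, 0.8 if 5% of each arm is affected, and 2.4 if 10% of SEL and 5% of placebo are. The first figure rests on constant hazard and is an upper bound at those rates. The affected shares in the other two are assumptions, and all three ignore other missing values and strata.

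The case for acting is the direction: with the primary response rates held fixed, multiple imputation favours SEL more as SEL events rise. In the tipping-point analysis the bias can go either way, and the shift mixes clinical failure with true missingness, so it cannot be read cleanly.

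**What to change.** In SAP 3.6.1, items 2 and 3, state that the Week 48 endpoint is set to non-response before imputation for:

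- any subject whose Week 48 window biopsy is absent because of death, transplant, a confirmed clinical event or open-label rollover; and
- any subject with F4 on Days 2 to 168 and no later biopsy in the window.

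Impute only the remaining missing values, and put the same rule in a data step before the Appendix 8 macro. Leave the observed-case and last-observation analyses as defined. It would help to report the number of reclassified subjects by arm.

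The cost is one SAP sentence and one data step. No new data are needed, and neither the primary analysis nor the sample size changes.
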